### **11.1            ADVERSE EVENTS**

Adverse events will be coded by system organ class and preferred term using the Medical Dictionary for Regulatory Activities, version 21.0 or newer.

An AE will be considered treatment-emergent adverse event (TEAE) if it started after the initiation of XEN implant related procedures.

An overall summary of subject incidences of TEAEs will be presented and will include experiencing the following:

- TEAE (ocular, non-ocular)
- Treatment emergent serious adverse event (TESAE) (ocular, non-ocular)
- TEAE with outcome of death (ocular, non-ocular)
- Study treatment (XEN) related TEAE (procedure related, device related)
- TEAE leading to study treatment discontinuation (XEN device removal)
- TEAE leading to study discontinuation

In general, the number and percent of patients in the Implanted Population reporting TEAEs will be tabulated by system organ class (SOC) in alphabetical order and by preferred term (PT) in descending order of incidence within the SOC, and further categorized by severity and causal relationship to the implant procedure or the device. If

more than 1 AE is coded to the same PT for the same patient, the patient will be counted only once for that PT using the greatest severity and strictest relatedness for the summarization by severity and relationship. These summaries will include:

- Non-ocular TEAEs by SOC, PT and severity grade
- Ocular TEAEs by SOC, PT and severity grade (SE, fellow eye)
- Non-ocular TEAEs by SOC and PT
- Ocular TEAEs by SOC and PT (SE, fellow eye)
- XEN procedure related TEAEs by SOC and PT
- XEN device related TEAEs by SOC and PT
- Incidence of common ( $\geq 5\%$  of patients) TEAEs by PT
- XEN procedure or device related adverse events occurring in  $\geq 2\%$  of the patients by PT
- Serious non-ocular TEAEs by SOC and PT
- Serious ocular TEAEs by SOC and PT (SE, fellow eye)
- TEAEs leading to XEN device removal by SOC and PT
- TEAEs leading to XEN device replacement by SOC and PT
- TEAEs leading to the study discontinuation by SOC and PT

Subject data listings will also be provided to support each summary table.

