2.2 Risk and Benefit

Glaucoma is the second leading cause of visual impairment and blindness worldwide. It results in a substantial economic burden for patients, their families, and society due to sizeable costs of disease management, vision loss, and lost productivity. Current treatment modalities for ACG have significant limitations regarding IOP-lowering effectiveness, adjunctive medication use, requirement for concomitant cataract surgery, complications, and cost. XEN provides effective, minimally invasive, long-lasting, safe, and durable IOP-lowering method through subconjunctival drainage. Use of XEN in patients with ACG might be associated with complications related to narrow angle including aqueous misdirection, cataract formation/progression, choroidal effusion, choroidal hemorrhage, chronic iritis, corneal edema, endothelial touch, flat anterior chamber, hyphema (> 1 week), Gel Implant blockage, iris atrophy, shallow anterior chamber, and suprachoroidal hemorrhage. These risks can be mitigated with appropriate concomitant surgical procedures that widen the angle (eg, cataract extraction, goniosynechiaelysis, iridoplasty). Furthermore, retrospective/case series data available to date on narrow and closed angle patients suggest similar safety as in patients with OAG. Taken together, the benefits outweigh the risks of XEN use in ACG patients.

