3.1 Study Objectives

The purpose of the trial is to evaluate the safety and IOP-lowering effectiveness of XEN in up to 65 patients with ACG.

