5.1 Number of Patients

Approximately 65 patients unilaterally implanted with XEN either as a stand-alone procedure or in combination with lens extraction. A subset of this population will include a maximum of 10 phakic patients (ie, will not undergo lens extraction at time of XEN surgery) and 10 patients with a history of trabeculectomy or glaucoma shunt implantation, to allow for a representative ACG patient population in the study. Sixty-five patients will be implanted to ensure at least 50 evaluable patients with 12 months of follow-up. Patients will be enrolled at approximately 15 clinical sites in the Asia-Pacific and European regions.

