## **6.0            PATIENT POPULATION**

The Implanted Population will include all patients implanted with XEN. The Implanted Population will be used for all primary and secondary effectiveness analyses and all safety analyses.

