  - Cells
  - Flare
  - Anterior Synechiae
  - Hypopyon
  - Hyphema
  - Other

Number and percent of patients in each of the above sub-categories will be presented using the worst severity observed in the SE by visit.

**Ophthalmoscopy Exam:** These exams will be performed at Screening, Baseline, Months 1, 3, 6 and 12/Early Exit. At each of these exams, any findings noted (yes, no, not

evaluable) in the ‘Vitreous’, ‘Optic Nerve Exam’, ‘Fundus Exam’, ‘Macula’, and ‘Retina Periphery’ will be recorded.

Number and percent of patients with findings noted in the above areas in the SE will be summarized by visit. Further, following data will also be collected associated with each of the above categories.

Vitreous: Severity (+0.5, +1, +2, +3, +4, not evaluable) associated with each finding: ‘Cells’, ‘Vitreous Haze’, ‘Vitreous Hemorrhage’, ‘Posterior Vitreous Detachment’ and ‘Other’. These data associated with the SE will be summarized in number and percent of patients format by visit.

Optic Nerve: ‘Disc Hemorrhage’ and ‘Other Disc Pathology’. Number and percent of patients with findings in each of these two areas in the SE will be summarized by visit.

In addition, Optic Nerve-Cup/Disc ratio data (numerical) of the SE will also be summarized by visit.

**Lens Status and Opacification**: Lens status findings questionnaire will be administered at screening, baseline, Months 1, 3, 6 and 12/Early Exit. Lens status at each assessment will be recorded as ‘Phakic’, ‘Pseudophakic’ or ‘Aphakic’. Lens status of the SE will be summarized by visit.

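### Study-eye cataract will be reported as a percentage of all implanted patients, which at the planned numbers is about 6.5-fold below the risk in the eyes that keep a natural lens

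*SAP*

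**What the plan says.** **Denominator.** SAP 11.1 states that "the number and percent of patients in the Implanted Population reporting TEAEs will be tabulated by system organ class (SOC" and, within that, by preferred term. SAP 6.0 defines the population: "The Implanted Population will include all patients implanted with XEN". Lens status plays no part, and no term is given its own at-risk denominator.

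**Cataract as a named risk.** Protocol 2.2 expects possible "complications related to narrow angle including aqueous misdirection, cataract formation/progression" and several further events.

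**Eyes that keep a lens.** Protocol 5.1 plans "Approximately 65 patients unilaterally implanted with XEN either as a stand-alone procedure or in combination with lens extraction", of whom "a maximum of 10 phakic patients (ie, will not undergo lens extraction at time of XEN surgery" may be included. Inclusion criterion 4 in Protocol 5.3 states the same cap as approximate. Exclusion criterion 23 rules out aphakia, so the remaining study eyes are pseudophakic after Day 1.

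**What is reported about the lens.**
- SAP 11.3 has a paragraph on lens status and opacification, but the only output it specifies is "Lens status of the SE will be summarized by visit". No opacification summary follows.
- Protocol 7.2 includes the lens in the slit-lamp examination. The slit-lamp summary in SAP 11.3 does not list it.
- SAP 10.1.3 uses lens status as a subgroup for the primary effectiveness outcome only.

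**The concern.** A pseudophakic eye cannot develop or worsen a cataract. When most of the denominator cannot have the event, the percentage describes the mixture of patients enrolled. It does not describe the risk for someone who receives XEN and keeps the lens, and that is the patient for whom the warning in Protocol 2.2 matters.

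Safety is a stated objective, and SAP 4.1.1 calls the study pivotal. A low cataract percentage could be read as reassurance about phakic eyes when it mainly reflects that few such eyes were enrolled. The effect is sharpest with no events: 0 of about 65 looks informative, whereas 0 of about 10 says little.

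**Working it through.** **Inputs**
- Implanted: about 65 (Protocol 5.1). The objective in Protocol 3.1 words it as "in up to 65 patients with ACG".
- Study eyes phakic after Day 1: at most 10 (Protocol 5.1), or at most approximately 10 (Protocol 5.3, criterion 4).
- Cut-offs for the short adverse-event tables: 5% for common events and 2% for procedure- or device-related events (SAP 11.1).
- Cataract rate: none is given in the documents, so the event counts below are assumptions.

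**Check of the interval method.** The plan's only precision figure is ±0.145 for 50 patients with an exact Clopper-Pearson interval (SAP 14.0). At 25/50 the interval is 0.3553 to 0.6447, a half-width of (0.6447 − 0.3553)/2 = 0.1447, which rounds to 0.145. The figure is reproduced, and the same method is used below.

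**Dilution factor.** With x study-eye cataracts, the at-risk rate divided by the tabulated rate is (x/n phakic) / (x/N implanted) = N implanted / n phakic. It does not depend on x, provided x > 0.

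| Implanted | Phakic after Day 1 | Factor |
|---|---|---|
| 65 | 10 | 6.5 |
| 65 | 8 | 8.1 |
| 65 | 11 | 5.9 |
| 65 | 12 | 5.4 |
| 60 | 10 | 6.0 |
| 50 | 10 | 5.0 |

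The first row is the planned case. The others are assumed departures from it.

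**Rates and exact 95% intervals by assumed event count**

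| Events | Of 65 implanted | Of 10 phakic eyes |
|---|---|---|
| 0 | 0% (upper limit 5.5%) | 0% (upper limit 30.8%) |
| 1 | 1.5% (0.0 to 8.3) | 10% (0.3 to 44.5) |
| 2 | 3.1% (0.4 to 10.7) | 20% (2.5 to 55.6) |
| 3 | 4.6% (1.0 to 12.9) | 30% (6.7 to 65.2) |
| 4 | 6.2% (1.7 to 15.0) | 40% (12.2 to 73.8) |

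For zero events the upper limit is 1 − 0.025^(1/n), which gives 5.5% at n = 65 and 30.8% at n = 10. SAP 11.1 specifies numbers and percentages, not intervals, so these limits are what a reader would calculate.

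**Cut-offs.** 5% of 65 is 3.25, so 4 patients are needed, equal to 4/10 = 40% of the phakic eyes. 2% of 65 is 1.3, so 2 patients are needed, equal to 2/10 = 20% of the phakic eyes. If the study eye supplies the only events, a cataract in 1 of 10 eyes at risk reaches neither short table.

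**The case against.** The strongest reply is that nothing here is wrong. Incidence among all implanted patients is a standard and valid description of the case mix studied. The pieces of the at-risk rate are also mostly on the page:
- SAP 11.1 tabulates study-eye ocular events by system organ class and preferred term, separately from the fellow eye and with no frequency cut-off, and supports each table with listings.
- SAP 11.3 gives the number of phakic study eyes at each visit.
- SAP 11.2.1 itemises cataract and clear lens extraction on Day 1.

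This stands in large part. What remains is that no table in the SAP text joins events to eyes at risk, so the reader has to assemble the rate.

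Three stronger readings are tempting, and the documents do not support them.
- A reader might infer that the understatement is at least 6.5-fold. It is not a lower bound, because both 65 and 10 are worded as approximate: 12 phakic eyes give 5.4, and 50 implanted with 10 phakic give 5.0.
- A reader might infer that cataract would drop out of the report. It stays in the full tables whatever its frequency. Three events in 65 patients (4.6%) miss the 5% table but enter the 2% table if judged related. The 5% table is also not split by eye, so fellow-eye cataracts could count towards it.
- A reader might infer that a table of change in lens opacity is simply missing. The documents describe no opacity grade, so it is not established that the data for one exist.

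Finally, SAP 4.0 places table specifications in a separate document, and SAP 11.1 presents its tabulation as the general approach. The point is therefore limited to what the SAP text specifies.

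**Conclusion.** The point holds as a gap in safety reporting, not as an error in the standard tables. At the planned numbers a non-zero study-eye cataract percentage will be about 6.5-fold below the rate in eyes that can have the event, or about 5- to 8-fold over the range examined. With zero events the two rates agree at 0% and the difference lies only in the upper limit, 5.5% against 30.8%.

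This rests on about 65 implanted patients, about 10 study eyes phakic after Day 1, and counting study-eye events only. Fellow-eye cataract lies outside the factor. The factor itself needs no assumed cataract rate; the event counts shown are illustrations.

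**What to change.** **SAP 11.1.** Keep the standard tables. Add one table of study-eye cataract formation or progression TEAEs as n/N with an exact 95% CI, with N = study eyes still phakic after the Day 1 procedure. Show it regardless of the 5% and 2% cut-offs; applying a 5% rule within about 10 eyes would be empty, since one event is already 10%. Do not take N from the baseline lens status in SAP 8.2, because eyes that have lens extraction on Day 1 are still phakic at baseline.

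**SAP 11.3.** In those same eyes, summarise whatever lens findings the eCRF captures, so that the paragraph delivers what its heading announces.

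**Cost.** One small table from adverse-event and lens-status data already collected. The SAP 11.3 addition depends on what the eCRF holds. The drawback is wide intervals with about 10 eyes, which the table should make plain.

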## 11.2 XEN PROCEDURE AND ASSESSMENTS

Following data related to XEN procedure and assessments will be summarized for patients in the Implanted Population.

### 11.2.1 XEN Surgical Assessment

- XEN procedure (XEN implant only, XEN and other procedures). Further breakdown the other procedures (Cataract extraction/phacoemulsification, Clear lens extraction, Goniosynechialysis, Iridoplasty, other)
- Target Quadrant location (Superior, Nasal, Inferior, Temporal)
- Antifibrotic used (Mitomycin, Other)
- Number of sclera channels (1, 2, ..., 6)
- XEN freely mobile under the conjunctiva (yes, no)
- Additional surgical maneuvers (yes, no)
- Post-implantation bleeding (yes, no)
- Bleb formation (yes, no)
- Surgical complications (yes, no). If yes, further breakdown by complication (Detached Descemet's membrane, Iris damage, Lens contact, Vitreous bulge or loss, Significant AC bleeding, Retrobulbar hemorrhage, Conjunctival perforation, Shallow anterior chamber with peripheral iridocorneal touch, Flat anterior chamber with peripheral iridocorneal touch extending to the pupil, Other)

### 11.2.2 XEN Bleb Assessment

- A bleb present (yes, no). If yes:
  - Bleb location (superior, nasal, inferior, temporal)
  - Bleb height (flat, low, medium, high)
  - Horizontal extent (0 to <1 clock hour, 1 to 2 clock hours, >2 to <4 clock hours, 4 or more clock hours)
  - Vascularity (avascular-white, avascular-cystic, mild, moderate, extensive)
  - If leak suspected, Seidel Test result (no leak, multiple pinpoint leaks, streaming leak)

### 11.2.3 XEN Implant Assessment

- Implant visible in the anterior chamber (yes, no, not evaluable). If yes:
  - Implant location (superior, nasal, inferior, temporal)
  - Implant length (mm)
- Implant visible in the sub-conjunctival space (yes, no). If yes:
  - Implant location (superior, nasal, inferior, temporal)
  - Implant length (mm)
- Implant contact (cornea, iris, other)
- Implant appear to be occluded (yes, no, not evaluable)

## 11.3 OTHER SAFETY PARAMETERS

**Pregnancy:** Pregnancy test results for females of childbearing potential will be listed.

**Device problems/malfunctions:** Number and percent of patients with device problems/malfunctions anytime during the study will be presented by reporting period the problem/malfunction occurred.

**Manifest Refraction:** The data associated with Sphere (+/-, measurement in Diopter), Cylinder (+/-, measurement in Diopter) and Axis (measurement in degrees) are collected at screening, baseline, Month 3 and Month 12/Early exit visit. Manifest refraction will be performed during any visit if BCVA reduction of  $\geq 2$  lines is observed since the last BCVA examination. These data will be summarized by visit.

**Best corrected visual acuity (BCVA):** Visual acuity exams will be performed at screening, baseline, and Months 1, 3, 6, 8, 10 and 12/Early exit. BCVA will be recorded in Snellen equivalent units. Number and percent of patients with BCVA of the SE falling in each level will be summarized by visit. In addition, BCVA will be categorized into 3 groups: 20/40 or better, <20/40 to 20/100, and worse than 20/100. Number and percent of patients falling into each group will be summarized by visit.

Line change in BCVA from baseline at each follow-up evaluation will be calculated using the following formula:

$$\text{Line change} = 10 \times [\log_{10} (20/d_{\text{follow-up}}) - \log_{10} (20/d_{\text{baseline}})]$$

where  $d_{\text{baseline}}$  = denominator of the Snellen equivalent unit at baseline,

$d_{\text{follow-up}}$  = denominator of the Snellen equivalent unit at follow-up

The logarithmic value in the formula above needs to be rounded to the nearest tenth before proceeding to the calculation of the line change. A positive value indicates an improvement, a negative value indicates a worsening, and a zero indicates no change. Line changes in BCVA from baseline will be summarized using the following categories: decrease of > 2 lines, decrease of 2 lines, decrease of 1 line, no change, increase of 1 line, increase of 2 lines, and increase of > 2 lines.

**Visual Field Test:** Visual field tests will be performed at baseline and at Month 12/Early Exit visits. Number and percent of patients with an abnormal visual field in SE will be presented by visit and abnormality condition (Enlargement of blind plot, Superior arcuate scotoma, Inferior arcuate scotoma, Paracentral scotoma, Nasal step, Central scotoma, Generalized depression, Temporal scotoma, or Other). Note that a patient may have more than one abnormality condition. Further, visual field mean deviation and change from baseline to Month 12/Early Term will also be descriptively summarized. A change (Month 12/Early Term – Baseline) in visual field mean deviation measured using the same program of > 3.0 dB will be categorized as ‘Better’, a change of -3.0 dB to +3.0 dB will be categorized as ‘no change’ and a change of <-3.0 dB will be categorized as ‘Worse’. Number and percent of patients belonging to each the three categories will also be presented.

**Pachymetry:** Contact pachymetry will be performed at screening and Month 12/Early exist. Three measurements of central corneal thickness and their average are recorded. These average values will be summarized by visit. Changes from screening to Month 12/Early exit visit will also be summarized.

**Gonioscopy:** Gonioscopy exams will be performed at screening, month 1, 6 and 12/Early Exit. The findings will be summarized by visit.

**Ocular Biomicroscopic Exam:** These exams will be performed at screening, baseline, Day 2, Day 8, Week 2, Months 1, 3, 6, 8, 10 and 12/Early Exit. At each of these exams, any findings related to Eyelids/Eyelid Margins/Lashes, Conjunctiva (Bulbar of

Palpebral), Cornea, Anterior Chamber, or Iris/Pupil are noted (yes, no, not evaluable) will be recorded. Number and percent of patients showing findings in each of the above areas will be summarized by visit. Further, associated with each eye, symptom severity data except for 'Iris/Pupil' will also be collected for the sub-categories described below:

- Eyelids/Eyelid Margins/Lashes:
  - Erythema
  - Edema
  - Other
- Conjunctiva:
  - Hyperemia
  - Edema
  - Subconjunctival Hemorrhage
  - Pterygium, encroaching on visual axis
  - Pterygium, not encroaching on visual axis
  - Other
- Cornea (Central, Peripheral, or Central and Peripheral):
  - Filaments
  - Infiltrates
  - Edema
  - Corneal Guttata
  - Endothelial Pigment
  - Keratic Precipitates
  - Neovascularization
  - Opacity
  - Stromal Haze
  - Other
- Anterior Chamber:
  - Cells
  - Flare
  - Anterior Synechiae
  - Hypopyon
  - Hyphema
  - Other

Number and percent of patients in each of the above sub-categories will be presented using the worst severity observed in the SE by visit.

**Ophthalmoscopy Exam:** These exams will be performed at Screening, Baseline, Months 1, 3, 6 and 12/Early Exit. At each of these exams, any findings noted (yes, no, not

evaluable) in the ‘Vitreous’, ‘Optic Nerve Exam’, ‘Fundus Exam’, ‘Macula’, and ‘Retina Periphery’ will be recorded.

Number and percent of patients with findings noted in the above areas in the SE will be summarized by visit. Further, following data will also be collected associated with each of the above categories.

Vitreous: Severity (+0.5, +1, +2, +3, +4, not evaluable) associated with each finding: ‘Cells’, ‘Vitreous Haze’, ‘Vitreous Hemorrhage’, ‘Posterior Vitreous Detachment’ and ‘Other’. These data associated with the SE will be summarized in number and percent of patients format by visit.

Optic Nerve: ‘Disc Hemorrhage’ and ‘Other Disc Pathology’. Number and percent of patients with findings in each of these two areas in the SE will be summarized by visit.

In addition, Optic Nerve-Cup/Disc ratio data (numerical) of the SE will also be summarized by visit.

**Lens Status and Opacification**: Lens status findings questionnaire will be administered at screening, baseline, Months 1, 3, 6 and 12/Early Exit. Lens status at each assessment will be recorded as ‘Phakic’, ‘Pseudophakic’ or ‘Aphakic’. Lens status of the SE will be summarized by visit.

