27. Visually significant cataract (ie, BCVA 20/40 Snellen equivalent using LogMar chart at screening and baseline) in the study eye that will not be removed at the time of XEN implantation
28. Study eye with best-corrected visual acuity (BCVA) worse than 20/100 (Snellen equivalent using LogMar chart) at screening and baseline; fellow (non-study) eye with BCVA worse than 20/200 at screening and baseline. A patient with a cataract in the study eye and BCVA worse than 20/100 in the study eye may be included if, in the opinion of the investigator, the patient is likely to have BCVA of 20/40 or better after cataract surgery that will be performed at the time of XEN implantation.

6. Procedures

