6.1.2 Baseline Visit

Baseline visit must be performed 5 to 7 days before the surgery. The following tests must be performed on the baseline visit prior to the initiation of preoperative corticosteroid treatment:

- Evaluation of inclusion/exclusion criteria
- Medical history, surgical history, ophthalmic history, and ophthalmic surgical history, including presence of ocular pathology and concomitant ocular medications (both eyes)
- Concomitant medications (systemic and ophthalmic [both eyes]) and procedures
- AEs
- Urine pregnancy test (for females of childbearing potential)
- Manifest refraction (both eyes)
- BCVA using LogMar chart (both eyes)
- Biomicroscopic slit lamp examination (both eyes)
- Diurnal IOP measurement (both eyes): Three IOP measurements taken over an 8-hour period on the same day approximately 4 hours apart, at Hour 0 (± 1 hour), Hour 4 = Hour 0 + 4 hours (± 30 minutes), and Hour 8 = Hour 0 + 8 hours (± 30 minutes). As scheduling permits, the patient must have approximately the same Hour 0 time of day throughout the study. IOP must be completed prior to ophthalmoscopy.
- Ophthalmoscopy (both eyes)

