7.2 Safety Measures

The following will be collected and recorded on the appropriate eCRF page(s):

- AEs: All AEs, from the moment the patient signs the Informed Consent Form, will be monitored and recorded in the patient's source documents. All events will be reported to the sponsor on an AE eCRF, including seriousness, severity, action taken and relationship to study treatment. If AEs occur, the first concern will be the safety of the study patient.

- Females of childbearing potential will have pregnancy tests performed. Pregnancy test kits will be provided by the site and will be administered according to the instructions provided with the tests.

Measures of ocular safety include:

Visual acuity: Visual acuity tests will be performed at all scheduled visits, as described in [Table 1-1](#). Manifest refraction using Snellen equivalent with a logMar chart (see Protocol Procedure Manual) will be performed at Screening, Baseline, Month 3, and Month 12/Exit. At all other visits, the visual acuity technician will use the last manifest refraction performed and determine the Snellen equivalent visual acuity using the logMar chart. If there is a 2-line or more reduction in visual acuity from the last BCVA performed, a repeat manifest refraction in both eyes and BCVA will be performed.

Pachymetry: Corneal thickness using ultrasound (contact) pachymetry will be performed on the central cornea. The same instrument will be used throughout the study for a given patient. Contact pachymetry will be performed after IOP measurement.

Visual field test: Visual field will be assessed using automated perimetry (using either Humphrey 24-2 full threshold program or SITA Standard). The same test methodology must be used throughout the entire study for a given patient.

Biomicroscopic slit lamp examination: Biomicroscopic examinations will be performed using a slit lamp. The examinations will include evaluation of the condition of the eyelids, conjunctiva (including assessment of bleb characteristics), cornea (including assessment for corneal stromal edema at the XEN Gel Implant location), anterior chamber, iris/pupil, and lens, and assessment of Gel Implant placement.

Gonioscopy: Iridocorneal angle assessments will include Shaffer grade; postoperative gonioscopy will include device displacement, malposition, movement, device contact with cornea and/or iris, and device tip occlusion.

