8.3.3 Other Effectiveness Analyses

8.3.4 Safety Analyses

Safety analyses will be performed using the implanted population. The number and percentage of patients reporting AEs will be tabulated regardless of causality. AEs, adverse device effects (ADEs), BCVA, line change in BCVA from baseline, biomicroscopic slit lamp, and ophthalmoscopy findings will be summarized by frequencies at each visit.

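### BCVA line change uses a baseline taken before any Day 1 lens extraction and pools eyes with and without it, so vision lost after surgery can be tabulated as improvement or no change

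*SAP*

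**What the plan says.** Safety is part of the study purpose (Protocol 3.1, SAP 5.0). Protocol 8.3.4 sets the BCVA reporting, visit by visit: "AEs, adverse device effects (ADEs), BCVA, line change in BCVA from baseline, biomicroscopic slit lamp, and ophthalmoscopy findings will be summarized by frequencies at each" […]. SAP 11.3 gives the detail: "Line change in BCVA from baseline at each follow-up evaluation will be calculated using the following formula". The formula is ten times the difference between two log acuities, follow-up minus baseline. On rounding: "The logarithmic value in the formula above needs to be rounded to the nearest tenth before proceeding to the calculation of the line change". On sign: "A positive value indicates an improvement, a negative value indicates a worsening, and a zero indicates no change". Results go into seven categories, from a decrease of more than 2 lines to an increase of more than 2 lines.

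The reference value is preoperative. Protocol 6.1.2: "Baseline visit must be performed 5 to 7 days before the surgery". On timing, SAP 11.3 says: "Visual acuity exams will be performed at screening, baseline, and Months 1, 3, 6, 8, 10 and 12/Early exit". No acuity is therefore scheduled between baseline and Month 1.

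Lens extraction may be done in the same session as XEN (Protocol 4.4.1, SAP 4.1.2). Exclusion 27 bars an eye whose visually significant cataract will be left in place. Exclusion 28 lets in a cataract eye worse than 20/100 if, in the investigator's opinion, "the patient is likely to have BCVA of 20/40 or better after cataract surgery that will be performed at the time of XEN implantation".

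SAP 11.3 also counts patients at each BCVA level, and in three acuity groups, at every visit. SAP 11.2.1 records whether cataract or clear lens extraction accompanied XEN. No BCVA table is split by it, and the subgroups in SAP 10.1.3 apply only to the primary effectiveness outcome.

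**The concern.** In an eye with a visually significant cataract at baseline, the reference acuity is partly a measure of the cataract. Removing the lens on Day 1 can add several lines, and Exclusion 28 expects exactly that for some eyes. Those lines then offset any later loss in the same eye, because every follow-up visit is compared with the same preoperative value.

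The protocol lists complications that can affect vision: choroidal effusion and hemorrhage, corneal edema and aqueous misdirection (2.2), hypotony maculopathy (Section 11) and vision loss with hypotony (6.1.3.2.1). A within-eye measure of acuity loss is how their visual cost would be quantified. If the only such measure carries a gain from lens removal and is pooled with eyes that had no such gain, the table leans towards a favourable picture on a stated objective.

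**Working it through.** The documents give no figure for BCVA change, so there is none to reproduce. The check applies the SAP 11.3 formula to assumed acuities.

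**1. Formula.** Line change = 10 × [log10(20/d_follow-up) − log10(20/d_baseline)], each log rounded to 0.1.

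**2. Rounded logs.** 20/20 = 0.0; 20/25 = −0.1; 20/40 = −0.3; 20/63 = −0.5; 20/100 = −0.7.

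**3. Assumed paths.** These are illustrations, not data from the documents.

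| Baseline → best postoperative → final | From baseline (as tabulated) | From postoperative best | Three-group table |
|---|---|---|---|
| 20/100 → 20/25 → 20/63 | 10 × (−0.5 + 0.7) = +2 | 10 × (−0.5 + 0.1) = −4 | moves from the best group to the middle group |
| 20/63 → 20/20 → 20/40 | 10 × (−0.3 + 0.5) = +2 | 10 × (−0.3 − 0.0) = −3 | stays in the best group |
| 20/40 → 20/20 → 20/40 | 10 × (−0.3 + 0.3) = 0 | 10 × (−0.3 − 0.0) = −3 | stays in the best group |

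The first two eyes are tabulated as an increase of 2 lines and the third as no change. Each lost 3 or 4 lines after its postoperative best.

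**4. Loss needed before it shows as a loss.** Take the first eye, with Month 3 as its best. A 2-line decrease from baseline needs a rounded log of −0.7 − 0.2 = −0.9. From −0.1 at Month 3 that is 10 × (−0.9 + 0.1) = −8, an 8-line fall.

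**5. How many eyes could be affected.** Eyes left phakic are capped at about 10 of about 65. So at least about 65 − 10 = 55 eyes (55/65 = 85%) are lens-extracted on Day 1 or already pseudophakic. This does not count the affected eyes: an already pseudophakic eye has no Day 1 cataract removal, and a clear lens may be extracted too. The number with a cataract-limited baseline cannot be derived.

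**6. What the other summaries show.** The level and group tables are separate counts at each visit. They register part of the loss in the first path, but one eye's gain can cancel another's loss, and no eye is followed over time. Protocol 7.2 requires repeat refraction and BCVA after a drop of 2 or more lines since the last BCVA, but the SAP plans no table of eyes that met this. Ocular adverse events (SAP 11.1) and slit-lamp and ophthalmoscopy findings (SAP 11.3) are tabulated, but they do not measure lines lost within an eye.

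**The case against.** The strongest reply is that vision safety does not rest on this one table. Absolute acuity is shown at every visit, visual field change is classed as better, unchanged or worse, and study-eye adverse events are tabulated by severity. No hypothesis is tested, the safety tables are descriptive, and SAP 4.0 leaves table and listing specifications to a separate document. All of this stands. A reader might infer that BCVA safety is judged only by line change; SAP 11.3 itself contradicts that. What remains is narrower: no other planned BCVA summary measures change within a patient.

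A reader might also infer that the plan hides harm caused by XEN, or that a better table would reveal it. The documents support neither. Lens removal and implantation share one session in a single-arm study, so no BCVA table can separate them.

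An eye entering at 20/200 and ending at 20/80 might be read as a masked loss. It gained 10 × (−0.6 + 1.0) = 4 lines and fell short of the expected 20/40, which is not loss after surgery. The three-group table already shows it below 20/40.

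Finally, the refraction used at Month 1 might seem to add to the favourable lean. Protocol 7.2 says: "At all other visits, the visual acuity technician will use the last manifest refraction performed". For a lens-extracted eye at Month 1 that would be the preoperative refraction, unless a repeat was triggered. An outdated refraction makes acuity look worse, so this is a separate matter. Protocol 6.1.4 must also be read alongside it: it calls for refraction for BCVA testing at scheduled visits, while 7.2 and Table 1-1 list only Months 3 and 12 after surgery.

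**Conclusion.** The point holds in this form: line change from baseline is the only planned within-patient BCVA change measure, its reference precedes any Day 1 lens extraction, and it is not split by that extraction. In eyes with a cataract-limited baseline, several lines lost after surgery can be reported as improvement or no change. The illustration of +2 tabulated against −4 from Month 3 follows exactly from the SAP formula, but its acuities are assumed. The overall size of the masking is unknown, because the documents give neither the number of Day 1 extractions nor the baseline acuities of those eyes. The primary effectiveness analysis is unaffected. This is a worthwhile, inexpensive improvement to a descriptive safety summary.

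**What to change.** In SAP 11.3:

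- Keep line change from baseline, but tabulate it separately for eyes with and without Day 1 lens extraction, using the procedure data recorded under SAP 11.2.1.
- Add one descriptive table for all eyes: lines lost at each later visit from the best earlier postoperative BCVA obtained with a manifest refraction (normally Month 3), with the number and percent losing 2 or more lines.
- State the limits with the table. Test-retest noise and the choice of the best value as reference add some apparent losses. Loss before the reference visit is missed; this matters because 13 of the 16 hypotony cases in the earlier US study (Protocol 2.1) occurred on Day 1. Loss in combined-procedure eyes cannot be assigned to XEN alone.

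Separately, reconcile Protocol 6.1.4 with Protocol 7.2 and Table 1-1 on when postoperative refraction is done. Footnote Month 1 BCVA in lens-extracted eyes where it was taken with the preoperative refraction.

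The cost is SAP wording and one or two tables from data already collected, with no new visits or assessments. The sponsor would also report a less flattering figure, since loss from a postoperative best is by construction less favourable than change from a preoperative baseline.
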